Cover page for clinicaltrials.gov

Study Title	Determining the Implicit and Rule-based Learning Ability of Individuals With Aphasia to Better Align Learning Ability and Intervention
NCT Number	05119023
Document Description	IRB approved protocol
Document Date	Document version date = 8/30/22

PARTNERS HUMAN RESEARCH COMMITTEE PROTOCOL SUMMARY

Answer all questions accurately and completely in order to provide the PHRC with the relevant information to assess the risk-benefit ratio for the study. Do not leave sections blank.

PRINCIPAL/OVERALL INVESTIGATOR

[name]

PROTOCOL TITLE

Determining the implicit and rule-based learning ability of individuals with aphasia to better align learning ability and intervention

FUNDING

NIH NIDCD R21 DC019203-01

VERSION DATE

Version 7: 8/30/22

SPECIFIC AIMS

Concisely state the objectives of the study and the hypothesis being tested.

The objective of this study is to examine learning in individuals with post-stroke aphasia (acquired language impairment). We aim to determine a behavioral phenotype of learning for people with aphasia (PWA), examining how cognitive-linguistic variables and stroke characteristics (lesion size and location) relate to learning.

To this end, the aims are as follows:

Aim 1. Determine the presence of selective deficits in observational (implicit) and rulebased learning in individuals with aphasia. Participants in our study will be stratified in to one of four learning profiles: learning under (a) both conditions, (b) rule-based conditions only, (c) observational conditions only, and (d) no condition. Pilot work conducted in eighteen individuals with aphasia has identified equal percentages of learners of type a, c and d (20% of pilot participants in each stratification) with 40% showing learning under rule-based conditions only, supporting the hypothesis that differences in learning profile arise among PWA.

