Aim 2. Determine the predictors of observational and rule-based learning, incorporating subject-specific measures of structural brain damage, aphasia severity, attention, verbal working memory and executive function. We will use regression models to determine predictors of observational learning and rule-based learning, evaluating findings against theoretical frameworks. We predict that preservation of the striatum and selective attention will contribute to observational learning ability. Preservation of the prefrontal cortex, verbal working memory and executive function are expected to contribute to rule-based learning ability.

BACKGROUND AND SIGNIFICANCE

Provide a brief paragraph summarizing prior experience important for understanding the proposed study and procedures.

Aphasia is an impairment in the expression or comprehension of language that results from stroke, traumatic brain injury or progressive neurological disease. Research has shown that speech-language therapy, the treatment for aphasia, can significantly improve people's ability to communicate. However, A major challenge facing the field of aphasia rehabilitation is the variable response to intervention; while some patients respond to therapy, others show limited progress.

Partners Human Subjects Research Application Form Version Date: October 15, 2014 One relatively unexplored possibility is that response to intervention is, in part, due to differences among how patients best learn, which we refer to as learning phenotype. Although learning phenotypes have been used to inform rehabilitation treatments in other domains, treatments for aphasia are currently selected almost exclusively based on language abilities with little to no attention to underlying learning abilities. Our overarching hypothesis is that poor alignment of learning ability and language therapy limits progress and contributes to the variability in outcomes.

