During aphasia rehabilitation, patients are guided to relearn language, reaccess language or regain functional use of language via therapies that involve stimuli, tasks, cues and feedback (see Horton, 2006). Consequently, the process of therapy implicitly engages many mechanisms of learning that need to be systematically considered in aphasia. Evidence is emerging to suggest that nonlinguistic learning is impaired in individuals with aphasia (Schuchard & Thompson, 2014; [name] & Kiran, 2013a; [name] & Kiran, 2013b); and furthermore, that PWA develop strategies less consistently and less effectively than non brain-damaged controls ([name] & Kiran, 2015). We suggest that the contribution of underlying cognitive systems is essential to relearning in aphasia and that understanding the behaviors associated with learning are critical for our understanding of the mechanisms of therapy and ways to better tailor treatment to individuals.

In aphasia, little is understood about how task and treatment manipulations impact patient behaviors and progress with therapy. We propose to thoroughly examine the behaviors of learning and the cognitive-linguistic and lesion characteristics that relate to learning, to characterize a phenotype of learning for individuals with aphasia, setting the foundations for intervention studies aimed at individually tailoring treatment and improving the predictability of outcomes.

RESEARCH DESIGN AND METHODS

Briefly describe study design and anticipated enrollment, i.e., number of subjects to be enrolled by researchers study-wide and by Partners researchers. Provide a brief summary of the eligibility criteria (for example, age range, gender, medical condition). Include any local site restrictions, for example, "Enrollment at Partners will be limited to adults although the sponsor's protocol is open to both children and adults."

Study Design

In this cross-sectional study, 75 participants will complete language and cognitive assessments and behavioral tests of learning. A subset of participants will also complete a structural magnetic resonance imaging (MRI) scan to obtain structural brain images.

Sessions 1 & 2 described above, may take 3 sessions. If an additional session is needed, participants may complete this session in person or over Zoom based on preference. Session 3 described above, may be broken into 2 sessions based on participant scheduling preference.

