Participants will be tested over three to five sessions during which they will complete: (a) behavioral testing, (b) structural scanning. We anticipate that behavioral sessions (a) and (b) will take around 6 to 7 hours to complete.

- (a) Behavioral testing: Participants will be asked to come to research facilities at the MGH-Institute of Health Professions for behavioral testing. During these sessions, participants will complete standardized cognitive-linguistic assessments and computer-based observational and rule-based tasks, that allow for collection of accuracy, response time and eye gaze data. Most participants are expected to complete behavioral tasks in two to three, two-hour sessions. Some participants may prefer to schedule shorter, and more frequent test sessions and this will be accommodated, and tasks that can be administered over Zoom without affecting data quality (such as those that do not collect response times) can be collected over Zoom if preferred by participants.
- (b) Structural scanning:-The majority of participants will also complete a structural magnetic resonance imaging (MRI) scan in a 3Tesla scanner at the MGH Athinoula A. Martinos Biomedical Imaging Center to obtain structural images of their brain.

In order to participate in brain scans, participants must:

- be safe to participate as determined by the MR eligibility criteria outlined under eligibility, and
- produce scores of learning on at least one behavior learning task that are above chance. Since brain scan data are being utilized to evaluate and predict learning profile, individuals must show learning on at least one task.

High resolution clinical MRI scans from hospitalizations may be available for some participants. These scans will be requested, and if judged to be of high quality (e.g. no evidence of motion artifact, whole brain coverage, axial slices with voxels smaller than 3mm) participants may not need to participate in the structural scan at the MGH Athinoula A. Martinos Center for Biomedical Imaging. Scanning will occur on a separate day or on one of the behavioral testing days.

Eligibility criteria are as follows:

- Be between the ages of 18 and 80 years of age
- Have aphasia due to left hemisphere stroke per report and need for speech language therapy
- Be in the chronic stages of aphasia, at least 6 months post onset of stroke
- Report pre-morbid native-speaker level fluency in American English

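### Research MRI is offered only to people who learn on at least one task, so Aim 2's lesion regressions are selected on their own outcomes and leave people who learn under no condition largely or wholly unrepresented

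*Combined protocol and SAP*

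**What the plan says.** Research Design and Methods, item (b) Structural scanning, allows the research MRI to participants who are MR-safe and who "produce scores of learning on at least one behavior learning task that are above chance". The reason given is: "Since brain scan data are being utilized to evaluate and predict learning profile, individuals must show learning on at least one task". The same section adds: "High resolution clinical MRI scans from hospitalizations may be available for some participants". These will be requested, and one of sufficient quality (examples are listed) may replace the research scan. Nothing says whether a clinical scan is used for someone who missed the learning criterion.

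The scope is stated broadly. Specific Aims: "We aim to determine a behavioral phenotype of learning for people with aphasia (PWA), examining how cognitive-linguistic variables and stroke characteristics". Aim 2: "Determine the predictors of observational and rule-based learning, incorporating subject-specific measures of structural brain damage". Background and Significance ends on the intention "to characterize a phenotype of learning for individuals with aphasia". Aim 1 sets out four learning profiles, the last two being "c) observational conditions only, and (d) no condition". On their frequency: "Pilot work conducted in eighteen individuals with aphasia has identified equal percentages of learners of type a, c and d", at 20% each, with 40% learning under rule-based conditions only.

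Data Analyses specifies a two-predictor observational model (spared striatum, attention) and a three-predictor rule-based model (spared prefrontal cortex, working memory, executive function). The outcomes are the SRT effect size, AGL test accuracy and rule-based test accuracy. The power section adds participants to cover attrition and people who do not learn.

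**The concern.** A regression whose sample depends on its own outcome describes the selected group, not the population the aim names. Here the people left out are those who fail every task. They are the extreme of the behaviour the study wants to explain, and arguably the group that bears most on its premise that learning ability contributes to variable response to therapy. If the lesion findings are reported for people with aphasia generally, a reader would take them to cover a group that contributed few images or none.

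**Working it through.** **1. How a participant enters Aim 2.**
- Both models in Data Analyses contain percent spared tissue, so an image is required.
- The research image requires an above-chance score on at least one task.
- The Aim 2 outcomes are the Aim 1 task scores.
- Entry by research scan is therefore a function of the outcomes.

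**2. Who stays and who goes.** This applies the pilot split to the 75 planned participants and assumes the scan criterion uses the Aim 1 learner rules.

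| Profile | Share | Of 75 | Research scan possible |
|---|---|---|---|
| (a) both | 20% | 15 | yes |
| (b) rule-based only | 40% | 30 | yes |
| (c) observational only | 20% | 15 | yes |
| (d) none | 20% | 15 | no |

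This leaves 75 − 15 = 60. Among them, 15/60 = 25% failed the rule-based task and 30/60 = 50% failed observational learning. Selection is therefore partial: low scores on a given task remain in that task's model, and only failure on everything is removed.

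**3. Precision of the 20%.** 0.20 × 18 = 3.6, so the count behind it was presumably 3 or 4. Exact (Clopper–Pearson) 95% limits:
- 3/18: 3.6% to 41.4%; × 75 = 2.7 to 31.1 people.
- 4/18: 6.4% to 47.6%; × 75 = 4.8 to 35.7 people.

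The number barred could plausibly be anywhere from about 3 to 36.

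**4. What an unrestricted offer would give.** The documents state no scan target. As an illustration, take 50, the sample size in the observational power statement. With 15 non-learners among 75, the expected number scanned is 50 × 15/75 = 10 (hypergeometric 95% range 7 to 13). Under the criterion, the number of research scans from this group is 0.

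**5. Whether extra enrolment cures it.** On pilot margins 60 people pass the criterion, against planned sizes of 50 and 49. The headcount can survive, with 60 − 50 = 10 to spare for MR contraindication, refusal or poor images. The missing group is still missing.

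**6. Whether a slope bias can be quantified.** It cannot. Take f² = .28, so R² = .28/1.28 = .219, with normally distributed latent scores correlated across tasks through their residuals. The rule-based slope then shrinks by about 9%, 14% and 20% at cross-task correlations of −.26 (implied by the pilot split), 0 and .3. Adding a floor at chance (assumed 40 items, accuracy .5 plus .2 per latent SD above threshold) reduces all three losses to roughly 1% to 3%. For the observational slope, the no-floor model gives +6% to −18%, depending on the correlation assumed. The documents report no cross-task correlation.

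**7. What above chance means for the scan.** The scanning section does not point to the Aim 1 rules, and the SRT rule is an effect size of 0.2 with no chance level. The rule-based threshold of 50% is the guessing rate for a two-way judgement. The AGL threshold of 25% is the guessing rate when both presentations must be correct (.5 × .5). Whether these are plain cut-offs or reference values for a binomial test is unclear. A participant who guesses throughout would be barred roughly 14% to 34% of the time under plain cut-offs and roughly 77% to 89% under 5% binomial tests. Both ranges assume 20 to 60 items and 48 to 120 SRT trials per block, counts the documents do not give.

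**The case against.** The criterion is disclosed and reasoned: only a subset is to be scanned, the rule is written down, and extra people are enrolled because non-learning limits interpretation. That stands as a description. However, no passage then limits Aim 2 to learners, and the interpretability argument is weak because people who failed a given task remain in its model.

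It can also be said that no planned model predicts the four-way profile, so the absence of profile (d) breaks no specified analysis. That is right. A reader might infer that a profile model has been made impossible, but Data Analyses plans separate regressions on each task's score. What remains is a conflict between the stated reason for the criterion, predicting learning profile, and a rule that denies one profile a research scan.

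Two further readings go too far. The clinical-scan route is not undefined: the scans are requested, quality examples are given and no learning condition is attached. Only their use for non-learners is unstated. Nor is all of Aim 2 closed to non-learners, since all 75 participants are to have cognitive and learning scores.

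**Conclusion.** The point holds in a limited form. Entry to the lesion regressions by research scan depends on the outcomes. As written, the lesion part of Aim 2 cannot speak to people who learn under no condition, except through clinical scans whose use for them is not stated. The affected share is about 20%, roughly 15 of 75. That rests on an 18-person pilot and on the scan criterion matching the Aim 1 learner rules.

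Aim 1 profiles, and any cognitive-only analysis of all participants, are unaffected. A reader might infer that the Aim 2 slopes are biased by a known amount or that planned power is lost. The documents do not support this, because the result depends on an unreported correlation and on how scores behave at chance. No slope or power figure should be attached to this point.

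**What to change.** Remove the learning criterion from the structural scanning section. Offer the available scans to MR-safe participants regardless of learning score, for example in enrolment order. State that usable clinical scans from non-learners are included, and define the Aim 2 population as everyone with a usable lesion map.

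The cost is an amendment to one eligibility criterion and a short statement of the analysis population. The number of scans need not rise, but some slots will go to people who did not learn. If scanning has already begun under the criterion, the analysis should identify participants scanned before and after the change.

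If the criterion is kept:
- restrict Aim 2's lesion conclusions to people who learn on at least one task;
- still use non-learners' clinical scans, at least descriptively;
- tie above chance in the scanning section to a stated rule for each of the three tasks.

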Test of Every Day Attention (TEA; Robertson et al., 2001)	Evaluates auditory sustained attention, visual and verbal working memory
Temple Assessment of Language and (Verbal) Short-term Memory in Aphasia (TALSA; Martin et al., 2018) listening span, synonymy triplet and lexical comprehension subtests	Evaluates lexical-semantic short-term memory and working memory
Berg Card Sorting Test (http://pebl.sourceforge.net/)	Evaluates executive function (self monitoring, flexibility, attention, shifting)
Northwestern Assessment of Verbs and Sentences (NAVS; Thompson, 2012) sentence production priming and sentence comprehension subtests	Evaluates grammatical abilities/syntax. Higher scores on canonical > noncanonical sentences indicate the presence of agrammatism
Villard Sustained Attention Task (Villard & Kiran, 2015)	Evaluates visual sustained attention

Tompkins Listening span task	Evaluates auditory-verbal working memory
(Tompkins et al., 1994)	

Brief overview of statistical methods

Aim 1. Determine the presence of selective deficits in observational (implicit) and rule-based learning in individuals with aphasia.

Observational learning tasks: Participants will complete two observational learning tasks: Serial Response Time (SRT) Observational learning and Artificial Grammar Learning (AGL) Observational learning.

For the SRT observational learning task (described below), responses are made via eye gaze into a visual area of interest (AOI). Reaction times (RTs) are recorded as the time between target onset and gaze fixation within the target AOI. A trial is considered incorrect if an eye fixation was made that does not correspond to the target AOI. RTs for correct trials are examined. Outlier RTs three standard deviations above the mean RT of each block will be removed. A score of learning will be computed by comparing RTs on the last (7th) sequenced block of trials with RTs on the following (8th) pseudorandomized block (Schwarb & Schumacher, 2012). A Cohen's *d* effect size (ES) of observational learning will be calculated for each individual participant that compares mean RTs on the final sequenced block (S7) and the pseudorandom block (PS8) using pooled standard deviations. Any participant producing a small ES of 0.2 or above (Cohen, 1988) will be classified as a learner in the observational learning condition.

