For the AGL Observational learning task (described below), data are collected on the accuracy of match, non-match responses during training computed as a percent correct. Data are also collected as a percent correct score in the testing phase. Each stimulus will be presented two times in testing and accuracy will be coded as 1 (correct) if on both presentations the participant made a correct response. If the item is classified incorrectly on 1 presentation or both presentations, the response for that item will be coded as 0 (incorrect). A threshold probability of 25% will be utilized to characterize performance as above chance and classify a participant as a learner under AGL Observational conditions.

Rule based learning task: For the rule-based task (described below), data are collected on the number of rules learned within the instruction period. Data are also collected on accuracy in testing. An accuracy score is computed for the test phase and is the dependent measure of rule learning. We will compute binomial chance probability. A threshold probability of 50% will be utilized to characterize performance as above chance and classify a participant as a learner under rule-based methods. Any participant whose score does not meet criterion, will be stratified as demonstrating selective weakness in rule-based learning.

Aim 2. Determine the predictors of observational and rule-based learning, incorporating subjectspecific measures of structural brain damage, aphasia severity, attention, verbal working memory and executive function.

Calculations of lesion volume and spared tissue. Implicit and rule-based learning are thought to engage partially overlapping brain networks that include the striatum, dorsolateral prefrontal cortex, medial prefrontal cortex, anterior cingulate, thalamus, medial temporal lobe, superior and inferior parietal cortex, occipital gyrus and cerebellum (e.g.,Destrebecqz et al., 2005; Paniukov & Davis, 2018; Peigneux et al., 2000; Reber, 2013; Schneyer et al., 2009; Squire, 1992; Willingham et al., 2002). The amount of spared tissue within regions of this network will be calculated based on previously established methods (Kiran et al., 2015; Meier et al., 2016; Sims et al., 2016). For each PWA a lesion map, in which the lesioned voxels are

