assigned a binary value (1 or 0), are normalized from native to MNI space (a standard brain space utilized in imaging studies). The individualized lesion map is subtracted from each brain region of interest (ROI) to yield the volume of spared tissue per ROI. The percentage of spared tissue in each region is calculated by dividing the volume of spared tissue by the total volume of the MNI atlas ROI. We will use MATLAB to identify the union of lesion maps and anatomical ROIs from the MNI template to compute lesion volume and percent spared tissue for each ROI. Percent spared tissue in ROIs will be entered into regression models evaluating predictors of learning.

Cognitive Linguistic Assessments: Language and cognitive assessments will be scored based on norms and methods of administration and scoring provided in testing manuals and publications.

Composite scores of sustained attention, executive function, and auditory-verbal working memory will be computed for entry into regression models.

Data Analyses: Linear regression models will be run to determine the predictors of learning. Separate models will be examined for SRT observational, AGL observational and rule-based and learning. The dependent variable for SRT observational learning will be Cohen's d effect size for the first round of learning computed in Aim 1. The dependent variable for AGL observational learning will be percent correct in testing computed in Aim 1. The dependent variable for AGL observational learning will be percent accuracy obtained in Aim 1. We anticipate that accuracy rates will fall between .2 and .8 which is recommended if accuracy rates are to be used as a dependent variable for a linear regression. If scores fall outside of this range, we will switch to a logistic regression model where number of successes and the total number of trials are incorporated into the analysis.

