- Participants will be instructed to look at the dot as it moves from shape to shape via audio and visual instructions
- For some study blocks, dot movement follows a pattern (sequenced blocks)
- For other study blocks, dot movement is pseudorandomized

The AGL Observational learning task is another classic test of implicit learning involving learning of ordered items through exposure (Schuchard & Thompson, 2017). Artificial grammars contain hierarchal dependencies, similar to the rules that govern word-order and syntax in natural language. Therefore, the artificial grammars may more evidently reveal learning deficits among

PWA compared to the relatively simple serial reaction time (SRT) task (Schuchard & Thompson, 2017). During the AGL task:

- Participants will be seated a comfortable distance from a computer screen
- In an exposure phase, participants will look at pictures of two to six geometric shapes on a screen
- Participants will judge if two pictures presented in sequence match or do not match
- Responses are made via button press
- After training, participants complete a testing phase
- In testing, participants are informed that geometric sequences followed a pattern. Participants will be shown sequences and must judge if sequences adhere to the pattern or not via button press

Rule-based learning task (~30 mins):

To evaluate rule-based learning, participants will learn rules underlying an artificial grammar that contains hierarchical dependencies similar to the rules that govern word-order and syntax in natural language (Saffran, 2001) but are expressed in non-linguistic form (e.g. with shapes). In the rule-based task:

- Participants will be seated a comfortable distance from a computer screen
- Two to six geometric shapes will appear on screen
- Through visuals and audio instructions, participants will be taught rules of the grammar
- Once a rule is taught, participants answer yes/no questions related to the rule (see figure for examples).
- At the end of training, participants will be shown sequences and must judge if sequences adhere to the rules or not via button press

Cognitive-linguistic assessments

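### The AGL learner rule takes 25% both-correct as chance, which holds only for unbiased, independent guessing; on a balanced test of 14 or more items a one-button responder passes even a one-sided 5% binomial test.

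*Combined protocol and SAP*

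**What the plan says.** In the combined protocol and SAP, under Brief overview of statistical methods, Aim 1, each AGL test stimulus is shown twice and "accuracy will be coded as 1 (correct) if on both presentations the participant made a correct response"; any other outcome is coded 0. The classification rule follows: "A threshold probability of 25% will be utilized to characterize performance as above chance and classify a participant as a learner". The description of the AGL task under study procedures gives the response format: "Participants will be shown sequences and must judge if sequences adhere to the pattern or not via button press".

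The rule-based task has its own rule: "A threshold probability of 50% will be utilized to characterize performance as above chance and classify a participant as a learner under rule-based methods". That paragraph also says "We will compute binomial chance probability", a statement the AGL paragraph does not make. Neither paragraph gives an alpha or a direction for the test.

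The label or the score is used in three places:

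- Aim 1 sorts participants into four learning profiles. The serial response time (SRT) task has a separate rule, by which a participant with a large enough effect size "will be classified as a learner in the observational learning condition". How the SRT and AGL labels combine is not stated.
- Under Structural scanning, to be scanned a participant must "produce scores of learning on at least one behavior learning task that are above chance".
- In the Aim 2 data analyses, "The dependent variable for AGL observational learning will be percent correct in testing computed in Aim 1".

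The documents do not give the number of AGL test items, the share that adhere to the pattern, or any check for response bias.

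**The concern.** A both-correct score on a two-button judgement depends on response style as well as on learning. Someone who prefers one button, or who answers the same sequence the same way twice without knowing the grammar, gets both presentations right more often than one time in four. On a balanced test 25% is then the lowest expected score for a non-learner with a fixed button preference, not a typical one.

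On a balanced rule-based test with single presentations, the same one-button responder scores 50%. That fails a binomial test against 50%, and fails a plain cut-off if the score must exceed 50%. The two rules therefore treat identical non-learning behaviour differently, and response style alone can produce an apparent difference between AGL and rule-based learning, the kind of contrast Aim 1 looks for. A false AGL label also counts toward the scan criterion, and the same bias-sensitive score appears to be the AGL outcome in Aim 2.

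**Working it through.** **Inputs from the documents.** Two presentations per item, both required correct; two response options; 25% for AGL and 50% for the rule-based task.

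**Assumptions.** Half the test items adhere; even lengths n from 8 to 60; where a test is applied, one-sided 5%. The plan states 0.05 only for the regression power analysis.

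**Reproducing the plan's figure.** Two independent, unbiased guesses give 0.5 × 0.5 = 0.25, which is the plan's 25%.

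**Expected score of other non-learners.**

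- *Button preference.* Someone who answers *adheres* with probability q, whatever the item, gets both right with probability q² on adhering items and (1−q)² on the rest. The average is ½[q² + (1−q)²] = 0.25 + (q − 0.5)². This gives 25% at q = 0.5, 29% at 0.7, 34% at 0.8, 41% at 0.9 and 50% at 1.
- *Repeating an answer.* Suppose there is no button preference, but the second answer copies the first with probability c and is otherwise a fresh guess. The expected score is 0.25 + 0.25c. At c = 0.4 the two answers agree with probability 0.4 + 0.6 × 0.5 = 0.7 and the score is 35%. At c = 1 it is 50%.

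**Reading A: plain cut-off, score above 25%.** With the score distributed Bin(n, 0.25), unbiased guessers pass 32–49% of the time over n = 8–60. A one-button responder always passes if the adhering share lies strictly between 25% and 75%.

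**Reading B: binomial test against 25%.** The cut-off is the smallest count whose upper-tail probability under p = 0.25 is at most 0.05. A one-button responder scores exactly n/2. For button preference, the score is the sum of Bin(n/2, q²) and Bin(n/2, (1−q)²); for full repetition it is Bin(n, 0.5).

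| Items | Cut-off | One-button score (tail under 25%) | Unbiased passes | q = 0.8 passes | q = 0.9 passes | Always repeats: passes |
|---|---|---|---|---|---|---|
| 14 | 7 | 7 (0.038) | 3.8% | 9.6% | 25.5% | 60.5% |
| 20 | 9 | 10 (0.014) | 4.1% | 14.7% | 43.6% | 74.8% |
| 24 | 11 | 12 (0.007) | 2.1% | 9.2% | 33.9% | 72.9% |
| 32 | 13 | 16 (0.002) | 3.8% | 21.7% | 66.7% | 89.2% |
| 40 | 16 | 20 (0.0006) | 2.6% | 20.6% | 70.4% | 92.3% |
| 60 | 22 | 30 (below 0.0001) | 3.0% | 35.1% | 91.5% | 98.6% |

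- The one-button responder fails at 8, 10 and 12 items (4, 5 and 6 correct against cut-offs of 5, 6 and 7) and passes at every even length from 14 to 60. At one-sided 2.5% the boundary moves from 14 to 18.
- Unbiased guessers pass 1.4–4.9% over 8–60 items, so the test does control them.
- Over even lengths 20–40, q = 0.7 passes 4–11%, q = 0.8 passes 9–28% and q = 0.9 passes 34–78%. Full repetition passes 73–93%, and the 35% repeater passes 18–37%.
- Over 8–12 items, q = 0.7 to 0.9 pass no more than 3%, the 35% repeater 8–11% and full repetition 36–39%.

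**Unequal split.** With 40% of items in one class and 60% in the other (n = 10 to 60 in steps of 5), pressing the majority-answer button passes the test at every length. Pressing the minority-answer button passes from 35 items up (14 correct, cut-off 14).

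**Rule-based task for comparison, Bin(n, 0.5), n = 8–60.** Unbiased guessers pass a plain above-50% cut-off 36–45% of the time and a one-sided 5% binomial test 1–5% of the time.

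**The case against.** The plan's 25% is the usual chance value for two two-option answers, and requiring both to be correct guards against single lucky guesses. On this view the point concerns robustness to particular kinds of non-learner; it is not a calculation error. That is a fair description, but on the plain cut-off reading even ordinary guessers are misclassified.

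Test length, split, alpha and direction are all assumed here, and the source is a brief overview in an ethics submission. The 14-item boundary does need an even count and a one-sided 5% binomial test. On short tests of 8–12 items the effect of button preference under that test is negligible, although full repetition still passes more than a third of the time.

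Pure one-button pressing and perfect repetition are extremes, and their frequency is unknown. Practice blocks, recorded training accuracy and ongoing data review might expose the most obvious cases. None of these is a stated exclusion rule, and a moderate preference could go unnoticed.

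The later consequences are also bounded. A false AGL label alters scan eligibility only for someone who passes neither other task. Aim 2 uses the score, not the label. An observational-only profile follows only under some ways of combining SRT and AGL. These points limit the weight of the concern but do not remove it.

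**Conclusion.** The concern holds and should be fixed. The 25% chance value is correct only for unbiased, independent guessing, and no stated step detects departures from that. A plain cut-off labels about a third to a half of unbiased guessers as learners. A 5% binomial test controls them, but on a balanced test of 14 or more items it passes every one-button responder, and at 20–40 items it passes most participants who always repeat their first answer.

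The arithmetic is firm given a balanced test and, for the 14-item boundary, a one-sided 5% level. The practical effect could be negligible or large, because the documents give neither the test length nor the frequency of such responding.

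**What to change.** 1. Classify AGL learners by a one-sided 5% within-participant permutation test that compares the number of *adheres* responses per item (0, 1 or 2) between adhering and non-adhering items. State the item count and the split.
2. State that the rule-based learner criterion is the upper one-sided 5% binomial limit for p = 0.5, not any score above 50%.
3. Keep AGL percent correct as the planned Aim 2 outcome and add hit rate minus false-alarm rate as a sensitivity analysis only. That difference can be negative, so it does not fit the plan's .2–.8 range check or its fallback to successes out of trials.

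The cost is protocol wording and a little analysis, since both answers to every item are already collected. In simulation the permutation test labelled at most 4.3% of non-learners as learners across 84 scenarios (7 lengths from 16 to 60; q = 0.5, 0.8, 0.9 and 1; c = 0, 0.4 and 1; 3,000 runs each), and no one-button responders.

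Fewer participants will be classed as learners than under a plain cut-off. Against the 5% binomial reading, detection of true learners (2,000 runs per case) was as follows:

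| Learner: *adheres* rate on adhering v other items | Items | Permutation | Binomial |
|---|---|---|---|
| Unbiased, 70% v 30% | 20 | 71% | 71% |
| | 30 | 90% | 79% |
| | 40 | 96% | 90% |
| Yes-biased, 90% v 60% | 20 | 58% | 76% |
| | 30 | 79% | 85% |
| | 40 | 90% | 95% |

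The lower detection of yes-biased learners is the real cost, although part of the binomial rate there reflects the bias itself. A lighter alternative is to report each participant's *adheres* rate and flag one-sided responders. That would address most button preference but would leave answer repetition untouched.
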